### **Inclusion/Exclusion Criteria**

The following criteria are required for study inclusion: 1) age 18 to 29 years; 2) identifies as male; 3) identifies as gay/bisexual or reports having sex with men in past 12 months; 4) identifies as Latino/Hispanic; 5) self-reports being HIV-uninfected; 6) resides in San Diego County, California; 7) speaks English or Spanish; 8) is willing and able to provide informed consent; and 9) reports at least one HIV risk factor as informed by Centers for Disease Control and Prevention (CDC) guidelines. MSM are at elevated risk for HIV if they report one of the following: 1) an HIV-positive sexual partner; 2) diagnosis of a bacterial sexually transmitted infection (STI) within the past 12 months; 3) engaging in

condomless anal sex with a non-monogamous partner in the past 12 months; 4) engaging in commercial sex work in the past 12 months; 5) injection of illicit drugs and sharing of injection equipment in the past 12 months; or 6) engaging in drug treatment for injection drug use in the past 12 months. Individuals will be excluded if they self-report being HIV-positive. The intervention is designed to meet the needs of MSM who self-report their gender identity as male, but other gender identities are allowed in the study. If a potential participant indicates that their gender identity is not “male” (e.g., transgender, non-binary, gender fluid), then the participant will be informed that the study was designed for cis-male MSM; and will then be invited to determine whether they feel that they will benefit from the study based on their gender identity. Participants who previously were prescribed or are currently taking PrEP will be included in the study. Participants are not required to seek care at FHCSO to be included in the study.

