### **Data Collection**

**Survey and Interview Data Collection.** Following informed consent, the research coordinator will administer self-report baseline surveys using Qualtrics in-person in the participant's preferred language of Spanish or English, assess time required to complete surveys, and note any participant difficulty in answering survey items. Participants will be asked to complete 3- and 6-month follow-up surveys using a mixed mode approach, consisting of an initial Qualtrics (online) survey followed by an emailed survey if the Qualtrics survey is not completed. At baseline, 3-month follow-up, and 6-month follow-up, participants will be asked to complete measures of PrEP knowledge, PrEP awareness, PrEP attitudes, PrEP barriers, PrEP efficacy beliefs, PrEP adherence, PrEP initiation, sexual behaviors, beliefs about medications, medication self-efficacy, mental health, substance use, and social support (see Table 1 for information regarding study surveys, including evidence of their validity and reliability). Self-report demographic information will be obtained at baseline. Self-report surveys assessing client satisfaction with PrEP-related healthcare services will be administered at 3-month and 6-month follow-up. Those randomized to PN will complete a self-report survey assessing satisfaction with the interpersonal relationship with the patient navigator at 3-months and 6-months. In addition, all participants randomized to PN will be contacted by telephone at 6-months to complete a key informant telephone interview to assess acceptability of the intervention; these key informant interviews will be conducted by members of the assessment team and not by PNs.

Measures were chosen following a literature review of existing validated instruments, and psychometrically validated instruments were chosen when possible. However, as PrEP was only recently

recommended for the prevention of HIV, there are few validated surveys measuring constructs related to PrEP. For these constructs, the team created new measures, adapting from existing scales when possible. Surveys not available in Spanish were translated using a dual panel approach.

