**Table 1: Description and Timing of Surveys and Health Record Data Collection**

Construct	Description of Measure	Source	BL	3 m	6 m	6m EHR
PrEP Knowledge	16-item self-report measure of knowledge related to PrEP, including use and effectiveness. Data are collected using a Likert scale.	Team developed	X	X	X	
PrEP Awareness	One survey question assessing awareness of PrEP. Categorical data are collected.	Team developed	X	X	X	
PrEP Adherence	2-item self-report survey assessing ability to take PrEP over the past 7 days, and frequency (%) with which PrEP was taken over the past 7 days. Data are collected using a Likert scale.	Team developed	X	X	X	
PrEP Attitudes	10-item PrEP Stigma and Positive Attitudes Measure assessing personal opinions about PrEP and people who use PrEP; 16 additional items assessing general attitudes and beliefs about PrEP use, provider comfort and medical mistrust related to PrEP use, side-effect concerns about PrEP use, disclosure concerns and social norms related to PrEP use, and sexual risk concerns about PrEP use. Data are collected using a Likert scale.	Mustanski et al., 2018; Pulsipher et al., 2016	X	X	X	
PrEP Barriers	5 survey items related to concerns about PrEP use, efficacy, and stigma; 5 additional items assessing potential access barriers to obtaining PrEP, including lack of health insurance coverage, difficulty finding a provider, and cost of PrEP. Data are collected using a Likert scale.	Golub et al., 2012; Pulsipher et al., 2016	X	X	X	
PrEP Efficacy Beliefs	2-item measure of beliefs regarding the efficacy of PrEP. Data are collected using a Likert scale.	Pulsipher et al., 2016	X	X	X	
Medication Self-Efficacy	4 items assessing self-efficacy to adhere to PrEP; adapted for PrEP use from the Self-Efficacy for Appropriate Medication Use Scale (SEAMS). Data are collected using a Likert scale.	Adapted from Risser, Jacobson, & Kripalani, 2007	X	X	X	
Beliefs about Medicines	Items from the Beliefs about Medicines Questionnaire (BMQ), including the BMQ-Specific subscale, a 10-item scale assessing representations of medications, and the BMC-General subscale, an 8-item subscale assessing beliefs about medicines. Data are collected using a Likert scale.	Horne, Weinman, & Hankins, 1999	X	X	X	

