PrEP-Related Health Care Received	Date(s) appointment scheduled for PrEP consultation; Date attended appointment for PrEP consultation; Date(s) health care provider wrote PrEP prescription(s); Date the first follow-up PrEP appointment(s) scheduled; Date(s) of follow-up medical appointment attended; Data recorded in EHR regarding adherence and discontinuation; other data regarding PrEP-related health care	Team developed				X

Abbreviations: BL = baseline; 3m = 3 month follow/up appointment; 6m = 6 month follow-up appointment; EHR = electronic health record; STI= sexually transmitted infection; PN = patient navigation

**MEMS Device Data Collection.** At baseline and 3-month follow-up, all participants will be asked if they have obtained a prescription for PrEP. Those who indicate that they have been prescribed PrEP and have taken at least one pill will be asked to track their PrEP adherence via a Medication Event Monitoring System (MEMS) device. A MEMS device is a standard prescription bottle that includes a larger lid containing a MEMS monitoring cap. During the baseline or at a 3-month follow-up visit, the research coordinator will give participants a MEMS device with instructions for its use. Participants will be instructed to place all PrEP pills into a MEMS container so when a pill is removed, the device will record date and time of removal of the medication dose using a small microcircuit. A medication “event” is removal of bottle closure, followed by replacement of closure. A study staff member will collect MEMS devices from participants in-person at the 3- and/or 6- month follow-up and connect them to a MEMS® Reader, which transfers data to a secured server via a secured web platform. Timing adherence will be calculated as percentage of time each participant took PrEP as prescribed by determining number of doses of PrEP taken at 24-hour intervals for a once daily PrEP regimen and dividing it by number of days adherence was monitored with MEMS.

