## Statistical Analysis Plan

**Qualitative data.** Qualitative data (key informant interviews, navigator qualitative notes, supervisor notes) will be saved in a text file to import into NVivo for analysis. The study PIs will review the qualitative data using a content analysis technique, which identifies emergent themes occurring during discussion. Code mapping will be used to develop a preliminary set of codes (themes) corresponding to each potential strength of the PN intervention as well as every potential aspect for improvement. Then, the co-PIs will independently code the remaining data and meet to discuss and achieve consensus in coding. Once coded, the data will be summarized by theme. These data will be used to modify the PN intervention, if necessary, or will provide further indication that the PN intervention should be tested in a larger scale study.

**Quantitative data.** All quantitative data will be summarized descriptively to determine aspects of the PN intervention that worked well and potential areas of improvement of the PN intervention. Our biostatistician will be blinded to intervention assignment for participants and will conduct statistical analyses using SAS 9.4. Univariate statistics will be conducted for outcomes measured at baseline and 6-month follow-up to describe sample characteristics between the two groups (UC versus PN). Attrition in the two groups will be compared. Characteristics of individuals with missing values and individuals with no missing values will be studied. Multiple imputation technique will be implemented and sensitivity analysis will be conducted to assess if missing data is at random. Assumptions of statistical tests will be evaluated. For assessing preliminary impact, the primary outcomes are seven behaviors associated with the PrEP care continuum (i.e., appointment scheduled for PrEP consultation; appointment attended for PrEP consultation; PrEP prescription received; PrEP prescription filled; PrEP initiated; self-reported PrEP adherence over the past seven days; and PrEP follow-up medical appointment attended).

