To test the preliminary impact of the intervention, a series of logistic regression models will be conducted, with each of the 6 binary PrEP continuum primary outcome variables set as a criterion: 1) appointment scheduled for PrEP consultation; 2) appointment attended for PrEP consultation; 3) PrEP prescription received; 4) PrEP prescription filled; 5) PrEP initiated; and 6) PrEP follow-up medical appointment attended. In addition, we hypothesize that receipt of the PN intervention will be associated with increased self-reported PrEP adherence over the past seven days (also a primary outcome variable). To test the preliminary impact on the two measures of self-reported PrEP adherence, we will conduct two linear regression analyses with intervention group assignment entered as the independent variable and each measure of PrEP adherence entered as the dependent variable. Potential demographic variables (e.g., age) will be assessed for inclusion in the models as well. Finally, linear mixed models will be conducted to examine changes in 1) barriers to PrEP-related care; 2) PrEP knowledge, 3) PrEP efficacy beliefs; 4) medication beliefs, 5) PrEP attitudes; and 6) medication self-efficacy. Linear mixed models allow us to account for the dependence of the repeated measures. Different covariance structures will be implemented and the information criterion such as AIC or BIC will be used for model selection. We hypothesize that participants randomized to PN will have greater engagement in PrEP continuum behaviors compared to participants randomized to UC. Since data analyses are exploratory, and there is not adequate statistical power to evaluate efficacy of the PN intervention, these tests can only provide information regarding data trends and effect sizes. If the study and PN intervention methods are found to be feasible and acceptable, a larger study with adequate statistical power will be conducted to appropriately evaluate the efficacy of the PN intervention.

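### Self-reported PrEP adherence (primary): baseline PrEP use will be collected but is not a planned covariate, so some precision is left unused; the score of a non-user should also be written down

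*Combined protocol and SAP*

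**What the plan says.** - **Who enrols.** Inclusion/Exclusion Criteria: "Participants who previously were prescribed or are currently taking PrEP will be included in the study". People not on PrEP enrol as well. The Randomization section describes blocks of 4 and mentions no stratification by PrEP use.
- **What is collected.** Data Collection says that at baseline, 3 months and 6 months "participants will be asked to complete measures of PrEP knowledge, PrEP awareness, PrEP attitudes, PrEP barriers, PrEP efficacy beliefs, PrEP adherence, PrEP initiation", among others. Table 1 describes adherence as a "2-item self-report survey assessing ability to take PrEP over the past 7 days", plus "frequency (%) with which PrEP was taken over the past 7 days. Data are collected using a Likert scale". Under MEMS Device Data Collection, at baseline and 3 months, "all participants will be asked if they have obtained a prescription for PrEP".
- **How adherence is analysed.** Statistical Analysis Plan: "we will conduct two linear regression analyses with intervention group assignment entered as the independent variable and each measure of PrEP adherence" as the dependent variable. The section adds that demographic variables, with age as the example, will be assessed for inclusion. It names neither baseline PrEP use nor baseline adherence.
- **Population, timing and missing data.** The opening summary sets ITT. The SAP says "Univariate statistics will be conducted for outcomes measured at baseline and 6-month follow-up" and "Multiple imputation technique will be implemented and sensitivity analysis will be conducted to assess if missing data is at random". It gives no score for a participant who is not taking PrEP.

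**The concern.** Someone already on PrEP at entry is much more likely than a non-user to report high adherence at 6 months. Baseline use should therefore be one of the strongest predictors of this outcome, probably stronger than age. With no stratification and about 30 people per arm, current users can divide unevenly between the arms by chance, and an unadjusted regression carries that imbalance into the estimated difference. The SAP says the tests can inform only on trends and effect sizes, so the precision of the effect size is what the pilot has to offer. A prognostic variable already planned for collection should not go unused.

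A second, smaller matter sits beside it. Many participants may not be on PrEP at 6 months. Zero is the natural answer on the frequency item, but the Likert coding is not given. The ability item has no obvious answer for someone who is not taking the drug. The size of the adherence effect depends on how these people are scored.

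**Working it through.** **Inputs.** From the documents: 60 participants, two arms, blocks of 4, so about 30 per arm. The sample size rests on a citation. No power, SD or effect size is given for adherence, so there is no planned figure to reproduce. Everything else below is assumed and shows size only.

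**Step 1: hand calculation for one case.** Assume 20% of each arm (12 of 60) are current users at baseline and 85% of them use PrEP at 6 months. Among the others, 10% start in UC and 40% in PN. Users' frequency has mean 80 and SD 20; non-users score 0. A group with proportion p on PrEP has mean 80p and variance p(80² + 20²) − (80p)² = 6800p − (80p)².

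- Baseline users: mean 68, variance 5780 − 4624 = 1156.
- Others, UC: mean 8, variance 680 − 64 = 616. Others, PN: mean 32, variance 2720 − 1024 = 1696.
- Within-group variance: UC 0.2×1156 + 0.8×616 = 724; PN 0.2×1156 + 0.8×1696 = 1588.
- Between-group variance: UC 0.16×(68−8)² = 576; PN 0.16×(68−32)² = 207.4.
- Unadjusted SE: √[(724 + 576 + 1588 + 207.4)/30] = 10.2.
- Adjusted, with common slope (60 + 36)/2 = 48: the unexplained between-group part is 0.16×12² = 23.0 per arm, so SE = √[(724 + 1588 + 46)/30] = 8.9.

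The cut is about 13%.

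**Step 2: simulation over a range.** 60 people, blocks of 4, 20,000 runs per scenario. Others start at 10% or 20% in UC and 40% in PN. Frequency among users is normal(85, 20) cut to 1–100; non-users score 0.

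| Baseline users | Persistence | SD unadjusted → adjusted | Cut |
|---|---|---|---|
| 12 | 85% | 10.18 → 8.90 (UC 10%) | 12.5% |
| 12 | 85% | 10.72 → 9.72 (UC 20%) | 9.4% |
| 12 | 60% | – | 4.1% and 2.3% |
| 3 | 60–85% | – | 0.3–3.5% |
| 20 | 60–85% | – | 3.6–17.2% |

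No scenario showed a loss, and the mean estimate moved by at most about 0.4 points. In sample-size terms the first two rows correspond to 60×(10.18/8.90)² = 78.5 and 60×(10.72/9.72)² = 73.0 people. Ordinary 95% intervals covered 94.5% to 95.3%, so robust intervals are not essential.

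**Step 3: chance imbalance.** With 12 current users among 60 and 30 per arm, the hypergeometric probability of an 8:4 split or worse is 0.333. With the slope of 48 from Step 1, an 8:4 split moves the unadjusted difference by (4/30)×48 = 6.4 points.

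**Step 4: why the non-user score is worth stating.** Suppose 6 of 30 UC and 15 of 30 PN participants use PrEP at 6 months. Those who would use it anyway average 90, and the 9 extra PN users average m, between 60 and 90.

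- All randomised, non-users at zero: 9m/30 = +18 to +27.
- Users only: (6×90 + 9m)/15 − 90 = −18 to 0.

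At m = 60 the PN users' variance is 20² + 0.4×0.6×30² = 616. The users-only SE is then √(400/6 + 616/15) = 10.4, so −18 lies 1.7 SE from zero. If instead PN raised all users from 80 to 90, users-only is +10 and all-randomised is 15×90/30 − 6×80/30 = +29, with no conflict of sign.

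**The case against.** **On the covariate.** The analyses are declared exploratory and underpowered, the omission causes no bias, and the gain depends on two unknowns: how many current users enrol and how many stay on PrEP. All of that stands. With 3 baseline users the gain is negligible. It limits how much weight the point can bear, but it does not argue against a change that costs one degree of freedom and produced no loss in any scenario.

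**On non-users.** A reader might infer that the adherence effect is undefined, that non-users will be dropped, that multiple imputation will invent adherence for them, or that the sign of the effect is at risk. The documents do not support this. ITT applies. The regressions are on assigned group, with no restriction to users. Where the authors wanted users only they said so: MEMS monitoring is limited to people who were prescribed PrEP and have taken at least one pill. The SAP nowhere treats non-use as missing, and its outcome summaries point to 6 months. The users-only figures in Step 4 therefore illustrate a reading that the plan does not state. The survey instrument and the registration data set, which are not in the text available, may also settle skip rules and timing. What remains is a missing sentence, chiefly for the ability item.

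**Conclusion.** This is a worthwhile improvement in precision at almost no cost; it does not correct a bias. A reader might take the missing covariate to make the comparison invalid, but with random allocation the unadjusted estimate remains valid and is only noisier.

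The gain is about 9% to 13% of the SD if roughly 12 current users enrol and 85% persist, and 0.3% to 17% over the range examined. These figures assume the uptake rates above, a 0–100 scale and non-users at zero on the frequency item. They were not worked out for the ability item, whose scoring for non-users is not stated.

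The non-user score, the separation of non-use from missing data and the 6-month time point are secondary clarifications, because the plan's general rules already lean the same way.

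**What to change.** **Main change.** Prespecify baseline current PrEP use (yes/no) as a covariate in both adherence regressions, in all randomised participants. Define it from the baseline survey answers on PrEP use; a blank, with no baseline report of PrEP use or prescription, counts as no. The cost is one degree of freedom and a sentence in the SAP. The data are already planned, and little is gained if few current users enrol or persist.

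**Accompanying clarification.**
- The adherence regressions use the 6-month responses.
- Participants reporting no PrEP in the past 7 days take the zero or lowest category on the frequency item.
- Non-use is not treated as missing and is not imputed; only responses that are truly missing are.
- Answers that contradict each other, such as a positive 7-day frequency with no dose reported since study start, are queried and not forced to zero.
- The SAP states the value a non-user takes on the ability item, so that both planned regressions stay in place.
- Adherence among users is shown by arm, with numbers, as a descriptive summary that is not a randomised comparison.

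The last item is needed because the zero-scored outcome mixes uptake with adherence. With 15 PN users at 50 and 6 UC users at 90, it gives 15×50/30 − 6×90/30 = 25 − 18 = +7 despite a 40-point drop among users.
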